Telehealth visits (conducted via phone or video conference) may be implemented by or with approval from the sponsor and per the clinical judgment of the investigator, where feasible and permissible by local policy.

How the assessments performed at each visit are collected (via on-site visit, home health care, or telehealth visit) must be recorded in the CRF.

Sample Collection and Handling

The actual dates and times of sample collection must be recorded in the CRF, laboratory requisition form, and the source documents.

If blood samples are collected via an indwelling cannula, an appropriate amount (1 mL) of serosanguineous fluid slightly greater than the dead space volume of the lock will be removed from the cannula and discarded before each blood sample is taken. After blood sample collection, the cannula will be flushed with 0.9% sodium chloride, United States Pharmacopeia (USP) (or equivalent) and charged with a volume equal to the dead space volume of the lock.

Refer to the Schedule of Activities for the timing and frequency of all sample collection, and visits to the study site:

- For the main study:
 - Visiting the site is required on Days 1, 2, and 28. All other visits as indicated in the Schedule of Activities may either be performed at the site or by designated study site personnel who visits the participant at home. A time window of +/- 1 day for both site and home visits is allowed as indicated in the Schedule of Activities, to ensure at least 2 visits per week at least 2 days apart and maximally 4 days in between blood samples. Between on-site visits, administration of study intervention will either be at home (including remote supervision of study intervention intake, if feasible) or participants may come to the site. MDs need to be taken approximately at the same timepoint every day. Follow-up visits on Days 40, 50, and 90 should take place within a window of +/- 2 days.
- For the PK substudy:
 - Participants will remain at the site during the first 12 hours on Days 1 and 28. Visiting
 the site is required on Day 2 and Day 3. All other visits (Day 29 and Day 32) may either
 be performed at the site or by designated study site personnel who visits the participant
 at home.

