9.4.3. Key Secondary Endpoint

The key secondary endpoint is defined as presence or absence of laboratory-confirmed symptomatic DENV infection between baseline and last day of dosing. Laboratory-confirmed symptomatic DENV infection is defined as having at least 2 solicited systemic AEs (see Table 3), of which at least one is a most common dengue symptom (ie, fever, headache/retro-orbital pain, myalgia, arthralgia, rash), lasting for ≥ 1 day and occurring within a ± -2 -day window around the positive PCR or NS1 test, between baseline and the last day of dosing.

The key secondary objective will only be assessed at the FA if a significant reduction in the number of laboratory-confirmed DENV infections in the primary study population is established for the HDR. The key secondary objective will be assessed by estimating the prophylactic efficacy of the intervention group(s) in preventing laboratory-confirmed symptomatic DENV infection in the complete study population together with the 80% one-sided lower confidence limit for this prophylactic efficacy. Depending on the result of the primary analysis for the LDR, the key secondary objective will be assessed by:

- 1. Comparing the pooled number of events on the HDR and LDR with the placebo regimen, if both active intervention groups showed a significant effect in the primary study analysis population.
- 2. Comparing the number of events on the HDR with the placebo regimen, if only the HDR showed a significant effect in the primary study analysis population.

Laboratory-confirmed symptomatic DENV infections will be analyzed similarly as the primary endpoint with the model adjusted for DENV infection at baseline as well.

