Unless stopped for futility at the IA, the study would continue till 36 DENV infections were observed in the primary study population and 24 symptomatic DENV infections were observed in the complete study population. Symptomatic DENV infections are defined as having at least 2 solicited systemic AEs (see protocol 1), of which at least one is a most common dengue symptom (ie, fever, headache/retro-orbital pain, myalgia, arthralgia, rash), lasting for ≥ 1 day and occurring within a ± 1 -2 days' time window around the positive PCR or NS1 test, between baseline and the last day of dosing ± 1 day. Both conditions on DENV infections and symptomatic DENV infections needed to be satisfied before recruitment was considered complete.

The study was prematurely ended before the IA on 02 October 2024 due to portfolio reprioritization., therefore no IA is performed and the analysis after this premature end will be considered as FA. This decision was not based on any safety concerns.

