5.3. Primary Endpoint(s) Analysis

5.3.1. Definition of Endpoint(s)

All samples will be tested by a DENV RT-qPCR with a qualitative output. A sample is considered positive for DENV RNA in case the result is 'target detected'.

In addition, all samples will be tested by the EUROIMMUN enzyme-linked immunosorbent assay (ELISA). The results of this test will be reported in relative units (RU)/ml and will be interpreted as follows:

- <8 RU/ml: negative

- ≥ 8 to <11 RU/ml: borderline

^{**} Up to 60 minutes after first study intervention intake

^{*} PK substudy/other participants

– ≥11 RU/ml: positive

A sample is considered DENV NS1 positive if the qualitative DENV NS1 result is positive (ie. quantitative DENV NS1 result ≥11 RU/ml). Samples are considered DENV NS1 negative for missing ELISA results and for borderline or negative qualitative ELISA results (ie. quantitative DENV NS1 result <11 RU/ml).

The primary endpoint is defined as presence or absence of a laboratory-confirmed DENV infection between baseline and the last day of dosing + 1 day. Presence of a laboratory-confirmed DENV infection is defined as a positive DENV RNA or DENV NS1 protein (ELISA) test result. Missing results between baseline and last day of dosing + 1 day will not be considered.

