5.4. Secondary Endpoint(s) Analysis

5.4.1. Key Secondary Endpoint(s)

5.4.1.1. Definition of Endpoint(s)

The key secondary endpoint is defined as presence or absence of laboratory-confirmed symptomatic DENV infection between baseline and last day of dosing + 1 day. Laboratory-confirmed symptomatic DENV infection is defined as having at least 2 solicited systemic AEs, of which at least one is a most common dengue symptom (see Table 3), lasting for ≥ 1 day and

occurring within a +/-2 days time window around the positive PCR or NS1 test. If a sample is missing and the next or prior available sample is positive for a DENV infection, the missing sample will be considered as positive for DENV infection as well. Consequently, solicited AEs observed within +/-2 days around the scheduled missing sample date will be considered as well as a confirmation of a symptomatic DENV infection.

Table 3: Solicited systemic AEs

- Retro-orbital pain*	- Fever*	- Fatigue	- Vomiting
- Abdominal pain	- Headache *	- Myalgia *	- Diarrhea
- Arthralgia*	- Nausea	- Loss of appetite	- Rash *

^{*} Most common dengue symptom

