5.4.1.3. Estimand

The key secondary estimand attributes are as follows.

Population

Healthy HHCs, aged 16 or 18 (depending on the legal age of consent in the jurisdiction in which the study is taking place) to 65 years inclusive who fulfil with one of the following conditions:

no evidence of current DENV infection at baseline (based on target not detected (TND) results for DENV RNA assay and, if available, a negative/borderline result for NS1 protein assays) and with at least 1 result for DENV RNA or NS1 protein assay available post baseline up to and including the last day of dosing + 1 day (ie. the primary study population),

or

 asymptomatic for dengue at screening, but with evidence of current DENV infection (based on positive results for DENV RNA or NS1 protein assays at baseline) (ie. the secondary study population).

Endpoint

Binary endpoint: presence or absence of a laboratory-confirmed symptomatic DENV infection between baseline and last day of dosing + 1 day.

Interventions

Depending on the result of the primary analysis:

- If a significant reduction in laboratory-confirmed DENV infections is established for the LDR in the primary study population: Participants on a high- or low-dose JNJ-64281802 regimen (combined), or matching placebo in a double-dummy fashion under fed conditions.
- If no significant reduction in laboratory-confirmed DENV infections is established for the LDR in the primary study population: Participants on a high-dose JNJ-64281802 regimen, or matching placebo in a double-dummy fashion under fed conditions.

Intercurrent Events

- Prohibited medication (when considered as major protocol deviation).
- Missed doses and dose interruptions: Missing a LD, 2 consecutive MDs, or 2 nonconsecutive MDs within a week.
- Overdose of study intervention.
- Wrong study intervention (when considered as major protocol deviation)

These intercurrent events will be handled using a "treatment policy strategy" (ie, data will be used as observed), with participants included in the study intervention group as randomized.

Population-level Summary

Calculated prophylactic efficacy (=1 - odds-ratio ≈ 1 - relative risk).

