5.4.2. Supportive Secondary Analysis

5.4.2.1. Symptomatic DENV infections

Supportive analysis will be done with the objective to evaluate the prophylactic effect of JNJ-64281802 with respect to the prevention of symptomatic DENV infection between baseline and last day of dosing + 1 day among HHC who have no evidence of current DENV infection at baseline (ie. the primary study population).

The same definition, significance level, attributes and analysis methods as for the key secondary endpoint will be used (see 5.4.1), with exception of the population attribute as the population is restricted to the primary study population.

No subgroup analyses will be done for this endpoint.

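### The key secondary missing-sample rule has no limit on consecutive missed draws, so one positive test can confirm symptoms 10 or more days away from it

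*SAP*

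**What the plan says.** Protocol 9.4.3 counts a symptomatic infection when at least two solicited systemic AEs, one of them a most common dengue symptom, last a day or more and fall in a 2-day "window around the positive PCR or NS1 test, between baseline and the last day of dosing". It has no rule for missing samples.

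SAP 5.4.1.1 keeps that definition, extends the period by one day after the last dose, and adds: "If a sample is missing and the next or prior available sample is positive for a DENV infection, the missing sample will be considered" positive. Symptoms within 2 days of the scheduled date of the missed sample then count as well. No maximum number of missed draws or days is given there, in the estimand (5.4.1.3), in the analysis methods (5.4.1.4) or in the list of changes (6.2), which does not mention the rule.

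Three other places bear on it:

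- The primary endpoint fills nothing: "Missing results between baseline and last day of dosing + 1 day will not be considered" (SAP 5.3.1).
- The key secondary population includes contacts "asymptomatic for dengue at screening, but with evidence of current DENV infection" at baseline (SAP 5.4.1.3), with no post-baseline sample required. A baseline positive can therefore be the prior available sample.
- The supportive analysis in the primary study population inherits the rule: "The same definition, significance level, attributes and analysis methods as for the key secondary endpoint will be used" (SAP 5.4.2.1).

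**The concern.** The rule looks to the nearest available sample, not the adjacent scheduled one. One positive therefore reaches across every missed draw until another sample was actually obtained. The rule is also satisfied by either neighbour, so an observed negative on one side does not stop filling from a positive on the other.

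Followed as written, this can label symptoms as laboratory-confirmed dengue when the only positive test was taken a week and a half or more away. That fits poorly with the reason SAP 6.2 gives for narrowing the complete study population, namely that laboratory data should be able to confirm that the symptoms come from a dengue infection. The rule can only add cases. With so few events, a single added case can change the key secondary result.

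**Working it through.** **Inputs.** Planned virology draws are on Days 1 (predose), 5, 9, 13, 17, 21, 25 and 28 (Protocol 1.3.2.2 and 1.3.2.3). The intended spacing is "at least 2 visits per week at least 2 days apart and maximally 4 days in between blood samples" (Protocol 8). The symptom window is 2 days either side of a positive or filled date (SAP 5.4.1.1). Dosing is assumed to run to Day 28, so the endpoint period ends on Day 29. There were 14 symptomatic events when the study was stopped (SAP 1). The SAP gives no figure for how often the rule is used, so there is none to reproduce.

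**Step 1: one case followed literally.** Day 5 is negative, Days 9, 13 and 17 are missed, and Day 21 is positive. For Day 9 the prior available sample is negative, but the next available one is positive, so Day 9 is filled. It lies 9 − 5 = 4 days after an observed negative and 21 − 9 = 12 days before the positive. Symptoms count from 9 − 2 = Day 7, which is 21 − 7 = 14 days before the test.

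**Step 2: reach by number of missed draws before a Day 21 positive.** The eligible days are the union of the 2-day windows.

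| Missed draws | Dates treated as positive | Symptom days that count | Number of days | Farthest from test |
|---|---|---|---|---|
| 0 | 21 | 19–23 | 5 | 2 |
| 1 | 17, 21 | 15–23 | 9 | 6 |
| 2 | 13, 17, 21 | 11–23 | 13 | 10 |
| 3 | 9, 13, 17, 21 | 7–23 | 17 | 14 |
| 4 | 5, 9, 13, 17, 21 | 3–23 | 21 | 18 |

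A positive drawn one day off schedule gives 5–7 days for one missed draw and 9–11 for two. Before a Day 28 positive the last interval is 3 days, so the reach is 3 + 2 = 5 days for one and 3 + 4 + 2 = 9 for two. After a baseline positive, missing Day 5 extends counting to Day 7 (7 − 1 = 6 days away), and missing Days 5 and 9 extends it to Day 11 (10 days away).

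**Step 3: no gaps.** The windows around Days 5 to 28 are 3–7, 7–11, 11–15, 15–19, 19–23, 23–27 and 26–30. They join without a break, so inside a filled run every day is eligible.

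**Step 4: what one event can do.** One event is 1/14 = 7.1% of the total. The arm split is not given. As an assumed illustration, take 2 HDR and 6 placebo events and an unstratified conditional binomial with equal arms (not the planned exact logistic model):

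- 2 vs 6: P(X ≤ 2 of 8) = 37/256 = 0.145
- one case added to HDR, 3 vs 6: P(X ≤ 3 of 9) = 130/512 = 0.254
- one case added to placebo, 2 vs 7: P(X ≤ 2 of 9) = 46/512 = 0.090

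Against the 20% one-sided level, one added case could reverse the result or strengthen it, depending on its arm.

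**The case against.** The rule applies equally to all arms of a double-blind trial, needs an observed positive and two qualifying symptoms, and contradicts no protocol text. Protocol 9.4 leaves technical detail to the SAP. The key secondary test runs only if HDR first succeeds on the primary endpoint. All of this stands, and it keeps the point small. Long runs of missed draws should also be uncommon: Day 28 is a required site visit, discontinuers have virology at withdrawal and follow-up, and any observed sample ends the run. A baseline positive carried to Day 29 would need full dosing with every draw missed, which conflicts with planned conduct.

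A reader might infer more than the documents support:

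- *That a Day 40 positive can fill a missed Day 28 draw.* Such samples exist ("Follow-up visits on Days 40, 50, and 90 should take place within a window of +/- 2 days", Protocol 8). But SAP 5.4.1.1 ties the endpoint to the dosing period plus one day, and SAP 1.2 puts the period in the same sentence as the test: "time window around the positive PCR or NS1 test, between baseline and the last day of dosing". SAP 5.5.1.5 and 6.2 treat infections after dosing separately. The natural reading excludes it. It is simply not stated for filled samples.
- *That the 4 to 7 days in Protocol 2 limits the distance from test to symptom.* That is the usual time to resolution, and a positive test can precede symptoms.
- *That dropping the protocol's Poisson sensitivity analysis removed the check on this rule.* That analysis concerned the primary endpoint, where nothing is filled.

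**Conclusion.** The point holds as a defect in a stated rule, at the level of a change worth considering. As written, SAP 5.4.1.1 can count symptoms about 10 days from the only positive test with two missed draws and 14 days with three, including symptoms two days after an observed negative. For one adjacent missed draw, at about 6 days, it is sensible. The reach figures rest on the planned draw days and on a literal reading of the rule. They say nothing about frequency: the documents give neither the number of missed draws nor the number of the 14 events that rely on filling, which may be zero. No bias toward or against the drug can be claimed.

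**What to change.** Replace the sentence in SAP 5.4.1.1 with: 'A missed scheduled sample is considered positive only if an observed positive sample (scheduled, unscheduled or withdrawal) lies between baseline and last day of dosing + 1 day, and no other scheduled sampling day lies between the missed date and that observed sample. A sample considered positive under this rule does not make any other missing sample positive.' A scheduled sample drawn within its visit window should be read as belonging to its nominal day.

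With Days 13 and 17 missed and Day 21 positive, Day 17 is still filled and symptoms on Days 15–23 count, but Day 13 is not filled. A baseline positive with Day 5 missed counts Days 1–7. No counted symptom is then more than 4 + 2 = 6 days from an observed positive (7 with the one-day visit window). Naming withdrawal and unscheduled samples matters because contacts hospitalised with warning signs are withdrawn, and their withdrawal sample may be the only positive near a missed draw.

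List the rule in SAP 6.2 as an addition to the protocol definition. Report the key secondary analysis and the 5.4.2.1 analysis also without the rule, with the number of events that depend on it by intervention group.

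The cost is two sentences, one line in 6.2 and one extra run of those two analyses. The downside is possibly slightly fewer counted symptomatic events.

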5.4.1.2. Level of Significance

If a significant reduction in the number of laboratory-confirmed DENV infections in the primary study population is established for the HDR, the superiority of JNJ-64281802 above placebo will be tested in the FA at 20% one-sided significance level.

5.4.1.3. Estimand

The key secondary estimand attributes are as follows.

Population

Healthy HHCs, aged 16 or 18 (depending on the legal age of consent in the jurisdiction in which the study is taking place) to 65 years inclusive who fulfil with one of the following conditions:

no evidence of current DENV infection at baseline (based on target not detected (TND) results for DENV RNA assay and, if available, a negative/borderline result for NS1 protein assays) and with at least 1 result for DENV RNA or NS1 protein assay available post baseline up to and including the last day of dosing + 1 day (ie. the primary study population),

or

 asymptomatic for dengue at screening, but with evidence of current DENV infection (based on positive results for DENV RNA or NS1 protein assays at baseline) (ie. the secondary study population).

Endpoint

Binary endpoint: presence or absence of a laboratory-confirmed symptomatic DENV infection between baseline and last day of dosing + 1 day.

Interventions

Depending on the result of the primary analysis:

- If a significant reduction in laboratory-confirmed DENV infections is established for the LDR in the primary study population: Participants on a high- or low-dose JNJ-64281802 regimen (combined), or matching placebo in a double-dummy fashion under fed conditions.
- If no significant reduction in laboratory-confirmed DENV infections is established for the LDR in the primary study population: Participants on a high-dose JNJ-64281802 regimen, or matching placebo in a double-dummy fashion under fed conditions.

Intercurrent Events

- Prohibited medication (when considered as major protocol deviation).
- Missed doses and dose interruptions: Missing a LD, 2 consecutive MDs, or 2 nonconsecutive MDs within a week.
- Overdose of study intervention.
- Wrong study intervention (when considered as major protocol deviation)

These intercurrent events will be handled using a "treatment policy strategy" (ie, data will be used as observed), with participants included in the study intervention group as randomized.

Population-level Summary

Calculated prophylactic efficacy (=1 - odds-ratio ≈ 1 - relative risk).

5.4.1.4. Analysis Methods

The key secondary hypothesis in this study is that JNJ-64281802 is superior to placebo with respect to prevention of laboratory-confirmed symptomatic DENV infection between baseline and last day of dosing + 1 day in the complete study population.

Depending on the result of the primary analysis for the LDR, the key secondary objective will be assessed by:

- 1. Comparing the pooled number of events on HDR and LDR with the placebo regimen, if both active intervention groups showed a significant effect on the primary endpoint (as described in Section 5.3).
- 2. Comparing the number of events of the HDR with the placebo regimen, if only the HDR showed a significant effect on the primary endpoint.

Laboratory-confirmed symptomatic DENV infections will be analyzed similarly as the primary endpoint with the model adjusted for both the stratification factor (region) and DENV infection at baseline (primary/secondary study population). This includes the subgroup analyses as described in section 5.3.4.

5.4.2. Supportive Secondary Analysis

5.4.2.1. Symptomatic DENV infections

Supportive analysis will be done with the objective to evaluate the prophylactic effect of JNJ-64281802 with respect to the prevention of symptomatic DENV infection between baseline and last day of dosing + 1 day among HHC who have no evidence of current DENV infection at baseline (ie. the primary study population).

The same definition, significance level, attributes and analysis methods as for the key secondary endpoint will be used (see 5.4.1), with exception of the population attribute as the population is restricted to the primary study population.

No subgroup analyses will be done for this endpoint.

5.5. Exploratory Endpoint(s) Analysis

5.5.1.1. DENV infections

For IgG antibodies the actual values (RU/mL) will be available. Collected unquantifiable data of apassessments on anti DENV IgG Immunology will be handled according to the rules summarized in Table 4.

Table 4: Data Handling Rules for anti DENV IgG Immunology Assessments

	Quantitative Limits			
DENV Parameter	I OD/		Imputed Val	ues
221112	LOD/ LLOQ	ULOQ	TND/ <lloq, (1)<="" td="">>ULOQ⁽²⁾	</lloq,>	>ULOQ ⁽²⁾
IgG antibodies (RU/mL) (4)	2 (LLOQ)	280	1 (<lloq, td="" td)<="">308	</lloq,>	308

⁽¹⁾ LOD/2 or LLOQ/2

Exploratory analysis will be done to evaluate the prophylactic effect of JNJ-64281802 with respect to the prevention of DENV infection among HHC who have no evidence of current DENV infection at baseline (ie. the primary study population) using different definitions of DENV infection:

- through increase of 1.5 in anti-DENV antibody between baseline and Day 40,
- through increase of 1.5 in anti-DENV antibody between baseline and Day 50,
- through increase of 1.5 in anti-DENV antibody between baseline and Day 90, on condition that the increase results in a value > 22 RU/mL (=cut-off level).

The cut-off for the increase in anti-DENV antibody might be updated during the analysis.

The same significance level, attributes and analysis methods as for the primary endpoint will be used (see 5.4.1).

⁽²⁾ ULOO+(ULOO/10)

No subgroup analyses will be done for this endpoint.

